7.6 Quarterly Phone Calls

Phone calls will be placed to the family every 3 months between clinic visits to collect data related to study outcomes, and also to continue to engage the family in the study and provide informational updates. If the final 16/17-year visit (Visit B) has occurred, but the child has not yet reached the age of 17 years, quarterly calls may continue until the 17th year. Questionnaires to be administered will collect data on respiratory symptoms, environmental exposures and diet, health care utilization, and medication use. These phone calls will continue many questionnaires from the original URECA study, in addition to new questions appropriate for the older age group.

7.7 Methacholine Challenge Visit

Participants who are unable to complete the methacholine challenge at their 14/15-year Visit A or Visit B will be asked to come to clinic for a separate visit. During this visit, questionnaires will be administered to assess for changes to the participant's health and medications. The full set of questionnaires for annual clinic visits is not expected, although some may be administered if previously missed. IOS and Spirometry will be performed, followed by methacholine challenge. If the participant does not meet criteria to perform the challenge, post-bronchodilator spirometry and IOS with reversibility may be completed, if not previously conducted at the 14/15-year time point.

7.8 Home Environmental Exposure Evaluation

At the 16/17-year Visit A, the family will be given a dust collection kit, which includes instructions on how to collect a dust sample (refer to the URECA V Dust Collection Instructions Handout). A combined dust sample from the participant's bedroom floor and the participant's bed will be collected. The room where the participant sleeps most nights will be considered the bedroom. Measuring templates will be used to delineate the areas to be vacuumed. Dust will be collected using a vacuum cleaner with a special dust collection filter attached. The dust collector will be placed into a sealable plastic bag and mailed back to the study center for temporary storage (frozen). Crude samples will be batched and shipped to a central laboratory by express mail for sieving, extraction, and analysis. The dust specimens will be assayed to measure the concentration allergens such as: Der p 1, Der f 1, Bla g 1, Bla g 2, Fel d 1, Can f 1, Alt a 1, and Mus m 1. Additional allergens of interest and markers of fungal and microbial exposure may be measured. In addition, the caretaker or participant will complete a dust collection questionnaire, which will be mailed back with the dust collector.

When problems arise with the family doing the environmental sample collections, staff may go to the home to collect the dust samples.

7.9 Additional Visits or Contacts

Additional visits or telephone contacts may be made for any of the following reasons:

1. A visit was conducted but 1 or more planned procedures were not completed, or a result was not obtained.

2. Contact information needs to be updated (no more often than every 6 months).

Any of the assessments listed above may be conducted at additional visits or by telephone (as appropriate)—either for the first time or for reassessment.

During the consent process, the participants will be asked to consent or assent to the possibility of additional visits or contacts as described in this section. No participant will be subjected to an assessment for which he or she has not provided written consent or assent, and no informed consent/assent form will contain any information that has not been approved by the IRB of record.

7.10 Re-contact of Subjects after Study Termination

The caretaker/guardian of the participant is asked during the informed consent process to indicate that contact for future research studies is permissible.

8 Assessment of Safety

8.1 Definition of an Adverse Event (AE)

The URECA study has been designated as an observational birth cohort study by the ICAC and DAIT. As such, this study involves minimal active intervention outside of the normal standard of care for the participant. No study drugs are used in the URECA study. Adverse events are limited to any occurrence or worsening of an undesirable or unintended sign (including an abnormal laboratory finding), symptom, or disease in a study subject that is specifically associated (probably, possibly, or definitely – defined in section 8.4.1.2) with a study procedure that is not part of the normal standard of care for the participant. In the URECA study, adverse events are those related to the blood draws, nasal sample collection, allergen skin testing, sputum collection, or pulmonary function tests not included as part of standard of care for this group of patients.

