1.3 Potential Risks and Benefits

1.3.1 Risks of Study Procedures

The URECA study has been designated as an observational birth cohort study by the CAUSE consortium and DAIT. As such, this study involves minimal active intervention outside of the normal standard of care for the participant. No study drugs are used in the URECA study. All risks of the URECA study are limited to study procedures, i.e. blood draws, nasal sample collection, allergen skin testing, sputum collection, or pulmonary function tests not included as part of standard of care for this group of patients.

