1.3.1.3 Spirometry

Spirometry can cause coughing or lightheadedness, which will go away shortly after the test is finished. The albuterol that is given during reversibility testing can cause increased heart rate and blood pressure, nausea, headache, and a jittery or nervous feeling. These symptoms usually resolve in less than an hour.

Participants will be asked to withhold their asthma medications for a period of time before the procedure depending on the medication. Withholding of asthma medications before testing may cause a worsening of asthma symptoms. Participants will be informed that they can take their asthma medications if needed, and the procedure will be rescheduled. Exact medications to

withhold, length of abstention and procedures are described in the URECA V Manual of Operations (MOP) for ICAC-07.

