5.1.9 Fitness Testing

The Six-Minute Walk Test will be used at the 14/15-year time point to assess the participant's level of fitness.¹⁰ For this test the participant is asked to walk around two cones placed in a hallway 60 meters apart at a fast pace for six minutes. The number of meters walked is measured, as well as the participant's pulse and respiratory rate. The participant is asked to rate his or her level of fatigue on a visual analogue scale.

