At the 14/15-year Visit B, questionnaires about the participant's physical health, habits, and environment will be administered. A brief physical examination will be conducted, to focus on ears, nose, throat, chest and skin. Urine samples will be collected for post-menarcheal female participants. BIA will be performed to assess adiposity. In addition, the Six-Minute Walk Test will be performed to assess fitness. Nasal lining fluid will be collected in addition to nasal epithelial cells. IOS and spirometry will be performed. Participants who were unable to conduct the methacholine challenge at Visit A will attempt to conduct the procedure at this visit, again with post-bronchodilator spirometry and IOS reversibility done if the participant does not meet the criteria for the challenge. If the methacholine challenge is not conducted at either Visit A or Visit B during this time point, it will be conducted at a separate visit to occur any time after the 14/15-year Visit B.

7.4 16/17-Year Clinic Visit A

At the 16/17-year Visit A, questionnaires about the participant's physical health, habits, and environment will be administered. Questionnaires pertaining to stress and mental health will also be administered. A brief physical examination will be conducted, to focus on ears, nose, throat, chest and skin. Urine and blood samples will be collected. Spirometry and sputum induction will be performed. Supplies and instructions for the home dust collection will be provided to the families.

7.5 16/17-Year Clinic Visit B

At the 16/17-year Visit B, questionnaires about the participant's physical health, habits, and environment will be administered. A brief physical examination will be conducted, to focus on

ears, nose, throat, chest and skin. Urine samples will be collected for post-menarcheal female participants. BIA will be performed to assess adiposity. Spirometry and impulse oscillation spirometry with reversibility will be performed. Exhaled nitric oxide will be measured.

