8.3 Death Not Related to Study Procedures

A death occurring in a study participant not associated with blood draws, nasal sample collection, allergen skin testing, sputum collection, or pulmonary function tests will be reported as a serious adverse event not related to study procedures. The reporting process will follow the SAE reporting process.

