8.5 Reporting Procedures

All adverse events related to the blood draws, nasal sample collection, allergen skin testing, sputum collection, or pulmonary function tests occurring during the study will be reported to the SACCC. The SACCC reports to the NIAID Medical Monitor who is responsible for passing the information on to the NIAID Data Safety and Monitoring Board (DSMB). Adverse events will be followed until resolved or considered stable.

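### The procedure list that defines adverse events omits the Six-Minute Walk Test, so a walk-related death would be labelled unrelated to study procedures and milder walk events have no clear mandatory reporting route

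*Protocol*

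**What the plan says.** The walk is a planned procedure. Section 5.1.9, headed Fitness Testing, states: "The Six-Minute Walk Test will be used at the 14/15-year time point". Participants are asked to "walk around two cones placed in a hallway 60 meters apart at a fast pace for six minutes". Section 7.3 places it at the 14/15-year Visit B, where "the Six-Minute Walk Test will be performed to assess fitness", and Appendix B lists it as the Fitness Test.

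The safety sections rely on a list of five categories that does not include it:

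- Section 1.3.1 on risks: "All risks of the URECA study are limited to study procedures, i.e. blood draws, nasal sample collection, allergen skin testing", followed by sputum collection and pulmonary function tests outside standard care.
- Section 8.1, closing sentence: "adverse events are those related to the blood draws, nasal sample collection, allergen skin testing, sputum collection, or pulmonary function tests".
- Section 8.3: a death "not associated with blood draws, nasal sample collection, allergen skin testing, sputum collection, or pulmonary function tests will be reported" as a serious adverse event that is unrelated to study procedures, through the SAE process.
- Section 8.5: "All adverse events related to the blood draws, nasal sample collection, allergen skin testing, sputum collection, or pulmonary function tests" go to the SACCC, which passes them to the NIAID Medical Monitor and so to the DSMB.

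Section 8.1 also has a wider sentence before the list. It ties an adverse event to any study procedure that is not normal standard of care for the participant. Section 8.4.1.2 then makes only events related to a study procedure, with a pointer back to 8.1, reportable.

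**The concern.** A list that decides what counts as an adverse event has to match the list of procedures performed. Here it does not. The missing procedure is six minutes of fast walking, in a cohort where section 3.2.1 reports that 29% met the asthma definition at age 7. Even questionnaires have a risk entry in 1.3.1; the walk has none.

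Two things are at stake. The first is a wrong label: 8.3 sorts deaths by whether they are associated with the five categories, so a death during or after the walk falls on the unrelated side whatever its cause. The second is uneven capture. A site that follows the general sentence of 8.1 would record a mild or moderate walk event, and a site that follows the list in 8.1 and 8.5 would not. Section 8.4.3 rests its light safety analysis on a historically low adverse event rate. A rate collected through this list would say little about the walk.

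**Working it through.** The plan states no figure on this point, so the check compares passages.

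**Step 1: is the walk on the list?** The list appears four times (1.3.1, 8.1, 8.3, 8.5) with the same five categories: blood draws, nasal sample collection, allergen skin testing, sputum collection and pulmonary function tests. The walk or fitness test is absent each time.

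**Step 2: could it count as a pulmonary function test?** The protocol keeps the two apart. Pre- and post-bronchodilator pulmonary function testing is 5.1.3 and covers spirometry and IOS. The walk is 5.1.9 and measures distance, pulse, respiratory rate and fatigue. Section 7.3 lists IOS and spirometry separately from the walk and gives fitness as its purpose. The walk is not covered by that category.

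**Step 3: is the list closed?** Section 1.3.1 introduces it as a restatement of the study procedures, not as examples. The closing sentence of 8.1 says what adverse events are in this study, also without marking the items as examples. Section 8.5 repeats it as the scope of reporting to the SACCC. The general sentence of 8.1 points the other way, so 8.1 is in tension with itself, and 8.4.1.2 refers back to 8.1 without resolving it.

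**Step 4: what happens to a walk-related event?**

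| Event | Result under the list | Other route in the protocol |
|---|---|---|
| Grade 1 or 2, for example bronchospasm treated on site | Outside the scope of 8.5 | General sentence of 8.1; investigator's judgment under 8.5.1; referral under 9.2.2 |
| Grade 3 or 4, related to a study procedure | Outside the scope of 8.5 | 8.5.1, within 15 days (Grade 3) or 7 days (Grade 4 serious event); it refers to study procedures without repeating the list |
| Urgent hospitalization or ICU transfer | Outside the scope of 8.5 | 8.5.1, within 7 days, with no procedure list |
| Death | Reported under 8.3, labelled unrelated to study procedures | 8.5.1, within 7 days; the label in 8.3 is unchanged |

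Section 8.2 defines an SAE as an adverse event with one of certain outcomes, so a narrow reading of 8.1 also narrows the SAE definition. The routes in the right-hand column reduce the practical effect of this but leave the text inconsistent. Under 9.2.1 the Medical Monitor acts on what the SACCC passes on, so a Grade 1 or 2 walk event that a site does not send would not be seen in that review.

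**Step 5: how many participants are exposed?** Section 10.5 gives 442 active participants at age 14, and the walk is scheduled once. Section 10.3 says more than 85% of expected visits were completed in recent phases. If that rate holds for this visit (an assumption), about 0.85 × 442 = 376 or more would attend. The protocol gives no adverse event rate for the walk, so no event count follows.

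**The case against.** The strongest reply is that oversight of serious events is largely intact. The general sentence of 8.1 covers the walk. Section 8.5.1 requires DSMB reports of deaths, urgent hospitalizations, ICU transfers and procedure-related Grade 3 and 4 events, and allows any other event to be reported on the investigator's judgment. Section 9.2.2 has the DSMB review any event that investigators, the SACCC or the Medical Monitor ask it to. Visit B also includes IOS, spirometry and sometimes methacholine challenge, so an event there might qualify as possibly related to a listed test. All of this stands, and it confines the gap to the label in 8.3 and to lower-grade events. It does not close the gap: judgment and referral are discretionary, and attribution to a neighbouring test would name the wrong procedure.

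Three stronger readings are tempting, and the protocol does not support them.

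- A reader might infer that no walk event could ever be reported, or that a death would be lost. The routes above show otherwise; for a death the fault is its classification.
- A reader might apply an assumed event rate to the 442 participants and count missed events. The protocol supplies no such rate, and the age-7 asthma figure does not provide one.
- A reader might extend the point to medication withholding, since 1.3.1.3 says "Withholding of asthma medications before testing may cause a worsening of asthma symptoms". But 1.3.1.1, 1.3.1.3 and 1.3.1.4 set out withholding risks under skin testing, spirometry and methacholine challenge. Worsening from withholding is therefore already described as a risk of listed tests, and nothing shows that sites would read it differently.

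**Conclusion.** The point holds as an internal inconsistency that should be corrected. The omission is certain from the text, and so is the literal result of 8.3. That lower-grade walk events lack a clear mandatory route to the SACCC depends on reading the closing sentence of 8.1 and the scope of 8.5 as operative. On the broader reading of 8.1 those events are covered, and the fault is then that the sections disagree.

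The effect is small in scale: one short procedure, done once, in at most 442 participants of an observational cohort without study drugs. No phenotype, lung function or sensitization estimate depends on it. The Manual of Operations and the Safety Management Plan named in the protocol were not available; they may give sites clearer instructions, but the protocol text would still need to agree with itself.

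**What to change.** Reconcile the sections in one of two ways. Either add fitness testing to the list in 1.3.1, 8.1, 8.3 and 8.5, or have 8.3 and 8.5 refer to any study procedure outside normal standard of care, as the general sentence of 8.1 does, and bring the closing sentence of 8.1 and the matching sentence of 1.3.1 into line. The second option keeps the standard-of-care limit and does not depend on keeping a list current.

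Add a fitness-test entry to the risk subsections of 1.3.1. Section 8.4.2 requires the related procedure to be recorded on the eCRF, so confirm that this field can record the walk.

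The cost is minor protocol wording, a check of one eCRF field and possibly a few more reported adverse events. No procedure, visit or analysis changes.

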8.2 Definition of a Serious Adverse Event (SAE)

A Serious Adverse Event (SAE) is defined as an AE resulting in one of the following outcomes:

- Death during the period of protocol-defined surveillance
- Life Threatening Event (defined as an event that places a participant at immediate risk of death)
- Inpatient hospitalization or prolongation of existing hospitalization during the period of protocol-defined surveillance
- Congenital anomaly or birth defect
- Persistent or significant disability/incapacity

Any other condition which, in the judgment of the investigator, represents a significant hazard, such as an important medical event that does not result in one of the above outcomes, may be considered a serious adverse event when the event jeopardizes the participant or requires medical or surgical intervention to prevent one of the outcomes listed above.

8.3 Death Not Related to Study Procedures

A death occurring in a study participant not associated with blood draws, nasal sample collection, allergen skin testing, sputum collection, or pulmonary function tests will be reported as a serious adverse event not related to study procedures. The reporting process will follow the SAE reporting process.

8.4 Methods and Timing for Assessing, Recording, Analyzing and Adverse Events

8.4.1 Methods and Timing for Assessment

8.4.1.1 Grading of Adverse Events/Serious Adverse Events

Each adverse event will be assessed for severity and classified into one the categories below:

- **Grade 1 (Mild):** Event requires minimal or no treatment and do not interfere with the participant's daily activities.
- **Grade 2 (Moderate):** Event results in a low level of inconvenience or concern with the therapeutic measures. Moderate events may cause some interference with functioning.
- **Grade 3 (Severe):** Event interrupts a subject's usual daily activity or functioning and may require systemic drug therapy or other treatment. Severe events are usually incapacitating.
- **Grade 4 (Life threatening):** Any adverse drug experience that places the participant, in the view of the investigator, at immediate risk of death from the event as it occurred.
- **Grade 5 (Death)**

8.4.1.2 Attribution of Adverse Event to Study Procedure

For the purpose of this study, only AEs related to a study procedure (Section 8.1) will be reportable and by definition will always be assessed as related. The degree of certainty about relatedness will be graded using the two categories below.

- **Definitely Related:** There is clear evidence to suggest a causal relationship, and other possible contributing factors can be ruled out. The clinical event, including an abnormal laboratory test result, occurs within a reasonable timeframe after study procedure(s) and cannot be explained by concurrent disease or other drugs or chemicals.
- **Possibly Related:** There is some evidence to suggest a causal relationship (e.g., the event occurred within a reasonable time after study procedure(s)). However, the influence of other factors may have contributed to the event (e.g., the subject's clinical condition, other concomitant events). Although an adverse event may be judged only as "possibly related" soon after discovery, it can be flagged as requiring more information and later be upgraded to "definitely related".

8.4.2 Recording/Documentation

Adverse events and serious adverse events related to the study procedures will be recorded on an appropriate eCRF. The event, the procedure to which it is related, start date, stop date, and severity of each reportable event will be recorded on the eCRF.

8.4.3 Analysis/Management

The rate of AEs has historically been low in this study; therefore, the primary analysis of AEs will occur by the medical monitor as described in Section 8.5. Additional management is not expected to be necessary.

8.5 Reporting Procedures

All adverse events related to the blood draws, nasal sample collection, allergen skin testing, sputum collection, or pulmonary function tests occurring during the study will be reported to the SACCC. The SACCC reports to the NIAID Medical Monitor who is responsible for passing the information on to the NIAID Data Safety and Monitoring Board (DSMB). Adverse events will be followed until resolved or considered stable.

8.5.1 Serious Adverse Event Reporting

Adverse event reporting requirements to the NIAID DSMB for this protocol are as follows:

- Investigators will submit a completed serious adverse event report to the NIAID DSMB within 7 days after becoming aware of a subject death, a potentially life-threatening (Grade 4) serious adverse event that is possibly or definitely related to study procedure(s), an urgent inpatient hospitalization or transfer to the ICU.
- Investigators will submit a completed serious adverse event report to the NIAID DSMB within 15 days after becoming aware of any Grade 3 (severe) adverse event that is possibly or definitely related to study procedure(s), or an inpatient hospitalization (other than elective), a persistent or significant disability/incapacity, or a congenital anomaly/birth defect.
- Investigators will report within 15 days on any other event or condition regardless of grade, which in their judgment represents an event reportable to the NIAID DSMB.
- Investigators will forward all safety reports and related communications to the NIAID DSMB within 15 days of receipt.
- A summary of all adverse events will be reported to the NIAID DSMB with a continuing review submission.

